6.5 Overdose

An overdose is defined as the accidental or intentional administration of any dose of a product that is considered both excessive and medically important.

All occurrences of overdose must be reported as an SAE (see [Section 6.1.1](#) for reporting details).

6.6 Potential Drug Induced Liver Injury (DILI)

Wherever possible, timely confirmation of initial liver-related laboratory abnormalities should occur prior to the reporting of a potential DILI event. All occurrences of potential DILIs, meeting the defined criteria, must be reported as SAEs (see [Section 6.1.1](#) for reporting details).

Potential drug induced liver injury in HIV-1 mono-infected subjects is defined as:

1. AT (ALT or AST) elevation > 3 times upper limit of normal (ULN)

AND

2. Total bilirubin > 2 times ULN, without initial findings of cholestasis (elevated serum alkaline phosphatase),

AND

3. No other immediately apparent possible causes of AT elevation and hyperbilirubinemia, including, but not limited to, viral hepatitis, pre-existing chronic or acute liver disease, or the administration of other drug(s) known to be hepatotoxic

6.7 Other Safety Considerations

Any significant worsening noted during interim or final physical examinations, electrocardiogram, x-ray filming, any other potential safety assessment required or not required by protocol should also be recorded as a nonserious or serious AE, as appropriate, and reported accordingly.

6.7.1 Toxicity Management

The link to the current grading system for specific AEs and laboratory abnormalities is located in [Appendix 3](#) (DAIDS; See Appendix 3).

6.7.1.1 Management of Elevations in Liver Transaminases

The following Table 6.7.1.1-1 summarizes the management of elevations in liver transaminases:

Table 6.7.1.1-1: Management of Elevations in Liver Transaminases Grade Level of AST or ALT Recommendations^a

Grade	Recommendation
Grade 1	None
Grade 2	none
Grade 3	Confirm elevation, evaluate for potential causes (including but not limited to alcohol or other substance abuse, concomitant medications, reactivation of existing or de novo infection with hepatitis viruses) consult with BMS Medical Monitor or designate as soon as possible.
Grade 4	Interrupt all study medications, evaluate for potential causes (including but not limited to alcohol or other substance abuse, concomitant medications, reactivation of existing or de novo infection with hepatitis viruses), monitor values frequently and consult with BMS Medical Monitor or designate as soon as possible. If Grade 4 is deemed related to study medication the subject must be discontinued from the study. Otherwise, if reinstitution of study therapy is considered, please obtain approval from the BMS Medical Monitor or designate.

^a If persisting (> Grade 1/2), evaluate for alternative etiologies, including alcohol use and viral hepatitis

6.7.1.2 Management of Renal Toxicity

Serum phosphate levels and creatinine clearance (CrCl; CCL: as calculated by the Cockcroft Gault Equation [see [Appendix 4](#)] or eGFR) should be monitored and managed as described in the Viread local package insert/label.²⁸ Dose interval adjustments of TDF (Viread) are permitted, as described in [Section 4.5.2](#).

6.7.1.3 Management of Hyperbilirubinemia

Most patients taking ATV experience asymptomatic elevations in indirect (unconjugated) bilirubin related to inhibition of UDP-glucuronosyl transferase (UGT). Hepatic transaminase elevations that occur with hyperbilirubinemia should be evaluated for alternative etiologies. Dose modification of ATV is not permitted. Subjects who experience unacceptable jaundice/scleral icterus should be discussed with the BMS Medical Monitor or designate to determine if subjects are to be discontinued from study. The investigator must contact the BMS Medical Monitor or designate prior to discontinuing any subject due to hyperbilirubinemia.

6.7.1.4 Gastrointestinal Toxicity Evaluation and Management Plan

Pre-clinical toxicology studies in rats and dogs (see [Section 1.4.1.2](#)) have suggested a potential for GI related toxicity with BMS-955176. This section provides general guidance to the Investigator on the evaluation and management of primarily upper gastrointestinal symptoms. The Investigator may contact the Medical Monitor to discuss evaluation and management (including interruption of ARVs or discontinuation of a subject) of any GI symptoms throughout the trial.

Table 6.7.1.4-1: GI Toxicity Evaluation and Management

HISTORY	For symptoms of all grades, a thorough history forms the foundation of proper evaluation and management. The following are potential manifestations of some GI clinical syndromes that may occur (possibly in combination) during the clinical trial.
Nausea and Vomiting	The investigator should attempt to identify the etiology of these symptoms (and whether it is intraperitoneal, extraperitoneal, medication related, infection related, or due to a metabolic disorder). ³³ Medications can cause nausea and vomiting acutely.
Dyspepsia	The Investigator should identify the presence of red flags (odynophagia, unexplained weight loss, recurrent vomiting, GI bleeding, jaundice, palpable mass or adenopathy, or family history of GI malignancy). Symptoms of dyspepsia could include early satiety, bloating, or belching. Additionally, atypical symptoms of dyspepsia could include: pharyngitis, asthma, bronchitis, hoarseness, chest pain, or abdominal pain.
Ulcerative Disease	Symptoms suggestive of ulceration often are intermittent over a period of weeks to months and may be relieved by eating or antacid use; ³⁴ penetrating ulcers become more acute with localized pain and may not improve with food. ³⁵ The development of perforation may be indicated by severe diffuse abdominal pain.
Other Clinical Syndromes	Additional diagnostic criteria for other GI disorders potentially encountered in the clinical trial are available elsewhere. ³⁶
PHYSICAL EXAMINATION	Physical examination should complement elements obtained from the history³⁴ Acutely, the investigator may assess for signs of intravascular volume depletion (eg, orthostasis) and/or aspiration of vomitus as appropriate. Abdominal tenderness and guarding may indicate inflammation. The presence of fecal blood can indicate mucosal damage (eg, from an ulcer). Complete evaluation of dyspepsia should include an oral examination (poor dentition or pharyngeal erythema) and lungs for wheezing.

Table 6.7.1.4-1: GI Toxicity Evaluation and Management

DIAGNOSTIC EVALUATION AND MANAGEMENT	A major goal in the diagnostic evaluation of a subject with upper GI symptoms is to quickly arrive at a final diagnosis without exposing the subject to unnecessary (invasive) testing; Investigators should exercise good clinical judgment ³⁵ in this regard. A major goal of therapy is directed at correcting the underlying identifiable medical or surgical abnormalities. Consultation (eg, gastroenterologist) is recommended as clinically indicated.
Grade 1 symptoms	Subjects may be treated symptomatically. If subjects develop dyspepsia alone, generally only limited and direct diagnostic testing should be performed. ³⁴ If the subject has dyspepsia they should limit alcohol, caffeine, chocolate, tobacco, other contributing concomitant medications (eg, NSAIDs) and eating directly before bedtime. A variety of OTC medications are available to address constipation and diarrhea as indicated. Please refer to Appendix 1 for Prohibited and Precautionary Therapies.
Grade 2 symptoms ^a	
Diagnostic testing may include but is not limited to the following (as clinically indicated):
 
 • Serum chemistries and assessment of hemoglobin if not recently performed. • Testing for Helicobacter pylori • Serologies (eg, celiac disease) • PCR for viruses (eg, CMV) • Iron panel or Vitamin B12 level 
For subjects who develop dyspepsia or are infected with H. pylori the use of H2 antagonists, PPIs, Sucralfate, and antacids are prohibited (see Appendix 1 Prohibited Medications). If such therapy is required, discontinuation from the trial is necessary. The use of antiemetic's (eg, Prochlorperazine) can be utilized as indicated. Management should be targeted at addressing the underlying pathology.

Grade 3 symptoms ^a	
Diagnostic testing may include but is not limited to the following (as clinically indicated):
 
 • The testing outlined above in Grade 2 • A fasting serum gastrin level can be obtained in cases of known ulcers refractory to therapy, a family history of the disease, or when surgery is required; of note, H. pylori ³⁵ can increase gastrin levels. • A barium swallow to detect ulcers • CT to identify gastrointestinal inflammation and a penetrating or perforated ulcer. • Upper endoscopy with biopsy as indicated in order to evaluate dyspepsia further (eg, mucosal injury, new onset unexplained dyspepsia in subjects > 55 y/o, or the presence of red flags). 
Management should be targeted at addressing the underlying pathology.

Grade 4 symptoms ^a	
Diagnostic testing may include but is not limited to the following (as clinically indicated):
 
 • The testing outlined above in Grade 2 and Grade 3 • An acute abdominal series • If a perforated ulcer is clinically suspected, surgical consultation may be necessary

Table 6.7.1.4-1: GI Toxicity Evaluation and Management

	Initial management can include correction of hemodynamic and electrolyte abnormalities as clinically indicated. After stabilization, management should be targeted at addressing the underlying pathology.
^a	For Grade 2-4 symptoms if any ARV is thought to have a direct causal relationship to the patient's gastrointestinal symptoms, the Investigator should consider discontinuing the subject from the study and performing an evaluation/management plan incorporating elements above. The Investigator can consider interruption of the potential offending ARV(s) but must balance this with the increased probability of development of viral resistance/lack of efficacy. As stated above, prior to discontinuing the subject from the study, attempts should be made to discuss with the BMS Medical Monitor unless the safety of the subject is acutely at risk.

7 DATA MONITORING COMMITTEE AND OTHER EXTERNAL COMMITTEES

Not applicable.

8 STATISTICAL CONSIDERATIONS

8.1 Sample Size Determination

This is an estimation study, without statistical testing, and hence there are no power considerations.

It is expected that response rate for the primary endpoint for all five arms will be somewhere around 80%. With this response rate, and 40 subjects per arm, an exact 95% confidence interval would run from roughly 64% to 91%.

8.2 Populations for Analyses

The following definitions are used in this document:

- Enrolled subjects: Subject who signed an informed consent form and were assigned a Patient Identification number (PID);
- Randomized subjects: Enrolled subjects who received a treatment assignment from the IVRS;
- Treated subjects: Randomized subjects who received at least 1 dose of BMS-955176 or TDF. (Also referred to as the mITT analysis set)

8.3 Endpoints

8.3.1 Primary Endpoint(s) Stage 1 and Stage 2

The primary endpoint for Stage 1 and Stage 2 is the proportion of subjects with plasma HIV-1 RNA < 40 c/mL at Week 24. This will be assessed with the FDA snapshot algorithm. This uses the last on-treatment plasma HIV-1 RNA measurement, within an FDA-specified visit window, to determine response.

8.3.2 Secondary Endpoint(s)

- The antiviral efficacy will be determined by the proportion of subjects with plasma HIV-1 RNA < 40 c/mL at Weeks 48 and 96 using the FDA snapshot algorithm
- The antiviral efficacy will also be assessed by the proportion of subjects with plasma HIV-1 RNA < 200 c/mL at Weeks 24, 48 and 96 using the FDA snapshot algorithm approach with positive response defined as HIV-1 RNA < 200 c/mL
- The emergence of HIV drug resistance among samples sent for drug resistance testing will be assessed using the most recent version of the IAS-USA list of HIV-1 drug resistance mutations
- Changes from baseline in \log_{10} HIV-1 RNA and in CD4+ T-cell counts, and changes in the percentage of CD4+ T-cells will be assessed using on-treatment laboratory results, and pre-specified visit windows
- The frequency of SAEs and AEs leading to discontinuation (DC) will be tabulated directly from the case report forms (CRFs). The summary will count the number of subjects that have at least one event
- The occurrence of new AIDS defining events (CDC Class C events) will be tabulated from the CRFs. The summary will count the number of subjects that have at least one event
- The steady-state plasma PK of BMS-955176 will be assessed using the intensive PK data, collected at Week 2 from a subset of subjects

8.4 Analyses

In general, categorical variables are tabulated with counts and percents. Continuous variables are summarized with univariate statistics (eg, mean, median, standard error).

Longitudinal analyses use pre-defined visit week windows. Unless otherwise specified, windows around planned measurement times are constructed based on the midpoint between planned study visits (ie, half the duration of time between study visits), and data are summarized at each scheduled visit.

For the calculation of descriptive statistics of observed data, subjects must have a baseline measurement to be evaluable for longitudinal tabulations of parameter values and changes from baseline.

Tabulations of the following endpoints present the number of unique subjects with an event: protocol deviations; interruptions of study therapy; non-study medications; adverse events; and laboratory abnormalities. Thus, multiple occurrences of the same event are counted only once per subject.

8.4.1 Demographics and Baseline Characteristics

The following demographic and baseline characteristics will be summarized by treatment arm and overall using the treated subjects:

- Demographics: age, race, ethnicity, gender, geographic region;

- Disease characteristics at baseline: plasma HIV-1 RNA level, CD4+ T-cell counts and percentages, CD8+ T-cell counts, HIV-1 subtype;
- Laboratory tests at baseline;
- Pre-treatment CDC Class C AIDS events;
- Prior medications

8.4.2 Efficacy Analyses

The efficacy analyses will be based on the treated subjects.

8.4.2.1 Primary Efficacy Analyses

The primary efficacy endpoint is the proportion of subjects with plasma HIV-1 RNA < 40 c/mL at the Week 24 snapshot within each stage. This endpoint is assessed with the FDA snapshot algorithm. The primary analysis will be based on a modified ITT (mITT) approach. A sensitivity analysis will be conducted using an observed values approach. The two approaches will be implemented as follows:

- Modified ITT: The numerator will be based on subjects with plasma HIV-1 RNA < 40 c/mL at Week 24. The denominator will be based on all treated subjects
- Observed values: Similar to the mITT approach, the numerator will be based on subjects with plasma HIV-1 RNA < 40 c/mL at Week 24. However, the denominator will be based on the treated subjects with plasma HIV-1 RNA at Week 24

Response rates will be tabulated by treatment arm (within the stage) with exact binomial 95% confidence intervals.

Subgroup summaries will be provided to examine the impact of baseline viral load. Subgroup summaries may be provided to examine the impact of other important covariates such as CD4+ count, sex, geographic region, etc.

At Week 24, a Time to Loss of Virologic Response (TLOVR) analysis will be conducted as a sensitivity analysis that complements the snapshot analysis. The following definition for virologic rebound will be used:

“For subjects that have been confirmed as having reached virologic suppression, by having two consecutive HIV-1 RNA readings below the assay limit of detection (40 copies/mL), virologic rebound is defined as confirmed HIV-1 RNA levels above the limit of detection. For levels above the limit of detection, confirmation consists of either two consecutive readings, or a single reading followed by loss to follow-up.”

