3.5 Discontinuation of Subjects following any Treatment with Study Drug

Subjects MUST discontinue investigational product (and non-investigational product at the discretion of the investigator) for any of the following reasons:

- Subject's request to stop study treatment
- Any clinical adverse event (AE), laboratory abnormality or intercurrent illness which, in the opinion of the investigator, indicates that continued participation in the study is not in the best interest of the subject
- Termination of the study by Bristol-Myers Squibb (BMS)
- Loss of ability to freely provide consent through imprisonment or involuntarily incarceration for treatment of either a psychiatric or physical (eg, infectious disease) illness
- Pregnancy (subjects should be discontinued in an appropriate manner)
- Repeat non-adherence by the subject with the requirements of the protocol or treatment (as determined by Investigator in consultation with the BMS Medical Monitor)
- Evidence of Hepatitis B or C infection
- Failure to achieve $> 1 \log_{10}$ c/mL decrease in HIV-1 RNA by Week 8
- Confirmed plasma HIV-1 RNA ≥ 1000 c/mL after Week 24
- Confirmed plasma HIV-1 RNA ≥ 200 c/mL after Week 48
- Emergence of genotypic and/or phenotypic resistance to any component of the study treatment regimen at any time after Screening
- Subject requires switching to any other ARV

- Development of pDILI (potential drug induced liver injury)
- Confirmed QTcB or QTcF value > 500 msec
- Confirmed second degree (Type II) or third degree AV block at any time during the study

In the case of pregnancy, the investigator must immediately notify the BMS Medical Monitor/designee of this event. The study drug will be permanently discontinued in an appropriate manner.

All subjects who discontinue study drug should comply with protocol specified follow-up procedures as outlined in [Section 5](#) (ie, perform an Early Termination [ET] visit). The only exception to this requirement is when a subject withdraws consent for all study procedures including post-treatment study follow-up (no such period exists in this study) or loses the ability to consent freely (ie, is imprisoned or involuntarily incarcerated for the treatment of either a psychiatric or physical illness).

If study drug is discontinued prior to the subject's completion of the study, the reason for the discontinuation must be documented in the subject's medical records and entered on the appropriate case report form (CRF) page.

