8.4.2.2 Secondary Efficacy Analyses

The following secondary endpoints will be summarized by treatment arm:

- Proportion of subjects with HIV-1 RNA < 40 c/mL at Week 48 and Week 96 using mITT and observed values

- Proportion of subjects with HIV-1 RNA < 200 c/mL at Week 24, 48 and 96 using mITT and observed values
- Change from baseline in \log_{10} HIV-1 RNA and in CD4+ T-cell counts, and changes in the percentage of CD4+ T-cells over time
- Newly emergent genotypic substitutions (using all on-treatment isolates) will be tabulated by treatment arm
- The newly emergent phenotypic resistance profile (using all on-treatment isolates) will be tabulated by treatment arm

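### The observed-values response analysis drops subjects whom the protocol's own virologic and resistance stopping rules removed, leaving < 200 c/mL at Week 96 nearly uninformative

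*Protocol*

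**What the plan says.** Protocol Section 8.4.2.1 makes the mITT snapshot the primary analysis: "The denominator will be based on all treated subjects". It then adds: "A sensitivity analysis will be conducted using an observed values approach". The two share a numerator ("Similar to the mITT approach, the numerator will be based on subjects with plasma HIV-1 RNA < 40 c/mL at Week 24") and differ only in the denominator: "However, the denominator will be based on the treated subjects with plasma HIV-1 RNA at Week 24". A second sensitivity analysis is named for Week 24 only: "At Week 24, a Time to Loss of Virologic Response (TLOVR) analysis will be conducted as a sensitivity analysis that complements the snapshot analysis".

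Section 8.4.2.2 applies mITT and observed values to < 40 c/mL at Weeks 48 and 96, and to the second threshold: "Proportion of subjects with HIV-1 RNA < 200 c/mL at Week 24, 48 and 96 using mITT and observed values".

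Section 3.5 lists mandatory reasons for stopping. The virologic ones are:
- no fall of more than 1 log10 by Week 8;
- the resistance rule: "Emergence of genotypic and/or phenotypic resistance to any component of the study treatment regimen at any time after Screening";
- once Week 24 has passed, a confirmed HIV-1 RNA of at least 1000 c/mL;
- a stricter limit in the second year: "Confirmed plasma HIV-1 RNA ≥ 200 c/mL after Week 48".

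A subject who stops has an Early Termination visit, and Section 3.5 notes that the study has no post-treatment follow-up period. Section 8.3.1 restricts the snapshot to on-treatment values inside the visit window.

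**The concern.** The protocol fixes both the denominators and the stopping rules, so their interaction is not detail left to a SAP. A subject stopped before the window for a virologic or resistance criterion has no on-treatment value in it. The observed-values analysis then treats that subject like someone who moved away, although the protocol removed the subject because treatment was failing. Nothing in Sections 8.4.2.1 or 8.4.2.2 returns such subjects as failures.

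At stake is the usefulness of the only alternative response-rate analysis that Section 8.4.2.2 names at Weeks 48 and 96. Sections 1.1.3 and 1.5 identify virologic failure and resistance as the particular risk of the unboosted ATV arms. An arm with more virologic stops can receive the larger upward shift.

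**Working it through.** **Plan's own figure.** Section 8.1 expects about 80% response with 40 subjects per arm and an exact 95% interval of roughly 64% to 91%. The Clopper-Pearson interval for 32/40 is 64.4% to 90.9%, so the figure is reproduced.

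**Formula.** Let N be treated subjects, x responders and d treated subjects with no value in the window. The mITT rate is x/N and the observed-values rate is x/(N − d). The protocol gives no rate for d, so it is varied over the 8 expected non-responders (N = 40, x = 32):

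| d | Observed values | Exact 95% CI |
|---|---|---|
| 0 | 80.0% | 64.4 to 90.9 |
| 2 | 84.2% | 68.7 to 94.0 |
| 4 | 88.9% | 73.9 to 96.9 |
| 6 | 94.1% | 80.3 to 99.3 |
| 8 | 100% | 89.1 to 100 |

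**Which rules can act before each visit** (Section 3.5 and Table 5.4.1.1-1)
- *Week 24:* only the Week 8 rule and the resistance rule are mandatory virologic stops. Up to Week 24, a value of 400 c/mL or more only prompts consideration of stopping.
- *Week 48:* confirmed values of 1000 c/mL or more, and 400 to 999 with resistance, are added. Subjects at 40 to 399, or at 400 to 999 without resistance, may stay.
- *Week 96:* confirmed values of 200 c/mL or more after Week 48 are added. Subjects at 40 to < 200 stay, with adherence reinforced.

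**Week 96, illustrative arms of 40.** V = stopped by a virologic or resistance rule before the window; O = missing for other reasons; L = on study at 40 to < 200 c/mL; U = on study at 200 or more, unconfirmed or awaiting results. All others are < 40 c/mL (32 in each row). The observed denominator is 40 − V − O. If virologic stops are kept as failures, it is 40 − O.

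| V, O, L, U | < 40: mITT | < 40: observed | < 40: stops kept | < 200: mITT | < 200: observed | < 200: stops kept |
|---|---|---|---|---|---|---|
| 4, 4, 0, 0 | 80% | 32/32 = 100% | 32/36 = 88.9% | 80% | 32/32 = 100% | 32/36 = 88.9% |
| 4, 2, 2, 0 | 80% | 32/34 = 94.1% | 32/38 = 84.2% | 85% | 34/34 = 100% | 34/38 = 89.5% |
| 4, 0, 4, 0 | 80% | 32/36 = 88.9% | 32/40 = 80% | 90% | 36/36 = 100% | 36/40 = 90% |
| 0, 4, 4, 0 | 80% | 32/36 = 88.9% | 32/36 = 88.9% | 90% | 36/36 = 100% | 36/36 = 100% |
| 3, 2, 2, 1 | 80% | 32/35 = 91.4% | 32/38 = 84.2% | 85% | 34/35 = 97.1% | 34/38 = 89.5% |
| 2, 0, 4, 2 | 80% | 32/38 = 84.2% | 32/40 = 80% | 90% | 36/38 = 94.7% | 36/40 = 90% |

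For < 200 c/mL, only U can produce an observed failure. Rows three and four show the loss of information: four virologic failures and four unrelated losses both give 100% observed. Keeping the stops separates them, at 90% and 100%. For < 40 c/mL, the L subjects remain as observed failures, so the rate is raised but reaches 100% only if nobody is retained with detectable RNA.

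**Between arms.** Take mITT 28/40 = 70% against 34/40 = 85%, a gap of 15 points. Arm Y has 1 virologic stop and 2 other losses, so observed values give 34/37 = 91.9%.
- If arm X has 7 virologic stops and 2 other losses: 28/31 = 90.3%, a gap of 1.6 points.
- If arm X has 2 virologic stops and 2 other losses: 28/36 = 77.8%, a gap of 14.1 points.
- With virologic stops kept as failures, both cases give 28/38 = 73.7% against 34/38 = 89.5%, a gap of 15.8 points.

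**The case against.** The strongest reply is that observed values is a supportive summary that answers a different question, namely suppression among those measured. It appears beside an mITT analysis that already counts every virologic stop as a failure. Emergent resistance is tabulated by arm, TLOVR is added at Week 24, and the futility comparisons in Section 8.4.7 use the snapshot response. No decision in the protocol rests on observed values. All of this stands, and it limits the point to a secondary presentation.

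Three stronger readings are tempting but not supported:
- *That every Week 96 observed rate tends to 100%.* Table 5.4.1.1-1 retains subjects at 40 to < 200 c/mL, so this is wrong for < 40 c/mL. Even for < 200 c/mL, unconfirmed values and subjects kept on study pending resistance results can remain as failures.
- *That arm differences will be hidden.* The collapse from 15 points to 1.6 needs an extreme split of 7 stops against 1, for which the protocol gives no basis. Section 1.1.3 cites a boosted-versus-unboosted ATV trial with 75% against 70% on TLOVR but 87% against 76% on the measure labelled VR-OC. If that denotes observed cases, the gap there widened from 5 to 11 points.
- *That the defect lies in never falling below mITT.* Any analysis with the same numerator and a denominator no larger has that property, including the repaired one.

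The objection does not remove the core. The exclusions are informative because of the protocol's own rules, and at Weeks 48 and 96 no other response-rate alternative is named.

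**Conclusion.** The point holds in limited form. The observed-values denominator discards subjects whom Section 3.5 removed for virologic failure or resistance. The distortion is small at Week 24, larger at Weeks 48 and 96, and makes < 200 c/mL at Week 96 nearly uninformative. With 32/40 responding, the rate rises from 80% to between 84.2% and 100% as 2 to 8 non-responders are excluded. How much of that comes from virologic stops is unknown, because the protocol gives no stopping or dropout rates.

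The conclusion assumes that the stop precedes the snapshot window, so that no on-treatment value falls inside it, and that Section 3.5 is followed. A reader might infer that the primary result or the staging decision is compromised. The documents do not support that: the mITT snapshot keeps these subjects as non-responders, and the futility tests use the snapshot response.

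**What to change.** In Sections 8.4.2.1 and 8.4.2.2, define the observed-values denominator as treated subjects with an HIV-1 RNA at the visit plus those who stopped before the window for a Section 3.5 virologic or resistance criterion, the latter counted as non-responders. Exclude only subjects missing for non-virologic reasons, and tabulate exclusions by arm and reason. Keep the mITT snapshot as primary. The stopping rules themselves need no change.

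The cost is wording and light programming, since the discontinuation reason and the Early Termination HIV-1 RNA are already collected. The downside is that observed-values rates become slightly less favourable. They will still be at or above mITT, so the analysis should not be presented as a test of the primary result in the unfavourable direction.
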